8.1.2. Postdiscontinuation Follow-Up Period Assessments

Postdiscontinuation short-term and long-term follow-up assessments will be conducted as described in the Study Schedule ([Attachment 1](#)). Adverse event (AE) information will be collected until at least 30 days after the last dose of study treatment. After the 30-day short-term follow-up visit, only new and ongoing SAEs deemed related to study treatment will be collected.

Long-term follow-up will continue as long as the patient is alive and has not withdrawn consent to follow-up or the study has completed (as defined in [Section 8.1.3](#)).

For patients who discontinue study treatment for any reason without objectively measured PD, imaging studies and tumor assessments are obtained every 6 weeks (± 7 days), irrespective of treatment cycles as calculated from randomization, until documented progression.

For patients that discontinue study treatment after objectively measured PD, the following information will be collected every 2 months (± 7 days) for the first 2 years, then every 6 months (± 14 days) until the patient's death, or overall study completion:

- details on all subsequent anticancer treatment (start/stop dates and treatments administered)
- first post-study treatment disease progression date
- survival status

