10.2.4. Resource Utilization

Investigators will be asked to document the use of best supportive care (BSC) measures, concomitant medications, transfusions, and treatment-related hospitalization days. Such assessments are to be taken throughout the study through the 30-day short-term postdiscontinuation follow-up visit.

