10.3. Safety Evaluations

Investigators are responsible for monitoring the safety of patients who have entered this study and for alerting Lilly or its designee to any event that seems unusual, even if this event may be considered an unanticipated benefit to the patient.

The investigator is responsible for the appropriate medical care of patients during the study.

The investigator remains responsible for following, through an appropriate health care option, AEs that are serious, considered related to the study, or that caused the patient to discontinue before completing the study. The patient should be followed until the event is resolved or explained. Frequency of follow-up evaluation is left to the discretion of the investigator.

The timing of all safety evaluations is shown in the Study Schedule ([Attachment 1](#)). [Table JGDJ.6](#) presents a summary of AE and SAE reporting guidelines. [Table JGDJ.6](#) also shows which database or system is used to store AE and SAE data.

Table JGDJ.6. Adverse Event and Serious Adverse Event Reporting Guidelines

Period	Types of AEs/SAEs to be Reported	Collection Database	Lilly Safety System
Baseline (pretreatment)	Preexisting conditions	x	
	All AEs	x	
	SAEs related to protocol procedures	x	x
Study treatment period	All AEs	x	
	All SAEs	x	x
30-day short-term postdiscontinuation follow-up	All AEs	x	
	All SAEs	x	x
Long-term postdiscontinuation follow-up	All SAEs related to protocol procedures or study treatment	x	x
Continued access period	All AEs	x	
	All SAEs	x	x
Continued access follow-up	All AEs	x	
	All SAEs	x	x
After the patient is no longer participating in the study (that is, no longer receiving study treatment and no longer in follow-up)	All SAEs related to protocol procedures or study treatment that the investigator becomes aware of		x

Abbreviations: AEs = adverse events; SAEs = serious adverse events.

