5.14.5. Hospitalizations and Transfusions

The frequency and percentage of patients with any hospitalizations experienced during the study treatment period or 30-day postdiscontinuation follow-up period will be summarized by treatment group. Hospitalization incidence rates will be compared between the treatment groups using Fisher's exact test. In addition, total number of days in hospital and admissions will be summarized and compared using the Wilcoxon rank sum test.

Note. Discharge date will be imputed with last contact date for hospitalizations that are still ongoing at time of analysis.

The frequency and percentage of patients with any blood transfusions received during the study treatment period or 30-day postdiscontinuation follow-up period will be summarized by treatment group. Transfusions will be further characterized by transfused blood product (for example, packed red blood cells, platelets, fresh frozen plasma, or whole blood). The proportions of patients having blood transfusions will be compared between the treatment groups using Fisher's exact test.

Details of hospitalizations and transfusions will be included in patient listings.

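### Open hospital stays are closed at an undefined last contact date with no cap at the 30-day visit, so a stay that is never updated can absorb months of survival follow-up

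*SAP*

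**What the plan says.** SAP 5.14.5 selects hospital stays by a window: "hospitalizations experienced during the study treatment period or 30-day postdiscontinuation follow-up period will be summarized by treatment group". It adds that "total number of days in hospital and admissions will be summarized and compared using the Wilcoxon rank sum test". A note then gives the rule for stays without a discharge: "Discharge date will be imputed with last contact date for hospitalizations that are still ongoing at time of analysis". The SAP does not define the last contact date and does not limit the counted days to the window that selects the stay.

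Protocol 10.2.4 asks investigators to document, among other resource items, "transfusions, and treatment-related hospitalization days", and sets the end of collection: "Such assessments are to be taken throughout the study through the 30-day short-term postdiscontinuation follow-up visit". Under Protocol 8.1.2, long-term follow-up then runs until death, withdrawal of consent or study completion, and safety collection narrows: "After the 30-day short-term follow-up visit, only new and ongoing SAEs deemed related to study treatment will be collected".

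**The concern.** For a patient still on treatment at data cutoff the rule does no harm: the last contact lies inside the period in which hospitalization is recorded. The difficulty is a patient who has left treatment, is in hospital at the 30-day visit, and is afterwards contacted for survival. The plan calls for no further recording of hospitalization days, yet the imputed discharge may be a contact many months later. The imputed length would then measure how long the patient was followed, not how long the patient was in hospital.

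At stake are the descriptive totals of hospital days by arm. A few such stays can dominate a mean or set the maximum. Because the added time is follow-up time, it would be larger in an arm whose patients are followed for longer.

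**Working it through.** The documents give no figure for hospital days, open stays or imputed discharges, so there is no planned figure to reproduce. The check has three steps.

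**1. Can a stay remain open at analysis?**
- Related events: ongoing related SAEs are still collected after the 30-day visit (Protocol 8.1.2, Table JGDJ.6), so a later discharge date can reach the data.
- Unrelated serious events: Protocol 10.3 tells the investigator to follow them ("The patient should be followed until the event is resolved or explained"), but Table JGDJ.6 limits long-term SAE reporting to those related to treatment or protocol procedures. No section expressly requires the discharge date.
- Progression-related events: Protocol 10.3.1.1 generally keeps these out of SAE reporting, so there is no SAE route to an update.

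An open stay is therefore possible, most plausibly when it is unrelated or progression-related.

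**2. Length of one open stay.** SAP 5.2.1 gives duration in days as end minus start plus 1, and a month as 30.4375 days. Take a visit on day 30 after discontinuation and a last contact *m* months later (*m* is assumed). A stay starting on day *s* lasts 30 − *s* + 1 days if closed at the visit, and 30 + 30.4375*m* − *s* + 1 days if closed at last contact.

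| *m* (months after visit) | Days added | Start day 25 | Start day 10 |
|---|---|---|---|
| 0 (closed at visit) | 0 | 6 | 21 |
| 2 | 60.9 | 66.9 | 81.9 |
| 3 | 91.3 | 97.3 | 112.3 |
| 6 | 182.6 | 188.6 | 203.6 |
| 12 | 365.3 | 371.3 | 386.3 |
| 24 | 730.5 | 736.5 | 751.5 |

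**3. Effect on an arm.** All inputs here are assumptions except the 230 patients per arm: 40% hospitalized, median stay 7 days (mean about 10.1), the same share of open stays in both arms, exponential residual follow-up with mean 12 months. The added mean per hospitalized patient is the share open times the mean residual days, here 12 × 30.4375 = 365.25:
- 2% open: 0.02 × 365.25 = 7.3, so 10.1 becomes 17.4
- 5% open: 0.05 × 365.25 = 18.3, so 28.4
- 10% open: 0.10 × 365.25 = 36.5, so 46.6

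With 230 × 0.40 = 92 hospitalized per arm, these shares are about 2, 5 and 9 stays.

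Now let one arm have mean residual follow-up of 12 / 0.723 = 16.6 months (505.3 days), with true stays identical. Simulation (1,500 runs per setting) gave mean days per hospitalized patient of 20.4 against 17.4, 35.3 against 28.2 and 60.6 against 46.0 at 2%, 5% and 10% open. The Wilcoxon rejection rate at a nominal 5% was 0.045 to 0.061 with imputed stays, over equal and unequal follow-up, against 0.046 to 0.056 without imputation. A few extreme values move a mean a long way and the ranks very little.

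**The case against.** The case on the other side is substantial.

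- **The trigger is narrower than it looks.** The rule applies to stays still ongoing at analysis, not to every stay open at the 30-day visit. A reader might infer that every such stay is inflated. The documents do not support that: related SAEs are still collected, serious events are followed to resolution, and the sponsor checks the eCRF data (Protocol 11). This stands. It restricts the problem to stays whose discharge is never entered.
- **Last contact need not mean a survival contact.** Read as the last contact at which hospitalization was assessed, it adds nothing. This also stands, but a rule that gives 6 days on one reading and 371 on another needs a definition.
- **Progression-related stays may not be in the data.** Protocol 10.2.4 speaks of treatment-related days, and Protocol 12.2.11 of hospitalizations due to AEs. That would narrow the gap. However, SAP 5.14.5 and the protocol synopsis refer to hospitalizations without that limit, so the gap is not closed.
- **A survival benefit would show up as more hospital use.** A reader might infer this and put the inflation at 1/0.723 = 1.38 times. The documents do not support a figure. The design hazard ratio concerns survival from randomization, not residual follow-up after discontinuation among patients in hospital; the ratio also needs exponential survival and ignores censoring at cutoff. The simulation uses it only to show direction.
- **The planned comparison is a rank test.** A reader might infer that the test is distorted. The simulation does not support that when the open share is equal in both arms. The median is also reported (SAP 5.2), and stays are listed by patient, so an implausible length would be visible.

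**Conclusion.** The concern holds in limited form. As written, the rule permits survival follow-up to be counted as hospital days, because it names an undefined date and sets no limit at the end of the period in which hospitalization is recorded. Three conditions must meet: the stay is open at the 30-day visit, its discharge is never updated, and last contact is taken as the last survival contact.

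Where they do, one stay gains about 183 to 365 days for a last contact 6 to 12 months after the visit. The harm falls on mean and maximum hospital days, more so in an arm with longer follow-up. The intervals, the share of open stays and the hospitalization rate are assumptions; the documents give none of them.

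Severity is minor. This is a secondary resource-use summary outside the multiplicity-controlled outcomes (SAP 5.6), with no bearing on OS, PFS, ORR or the main adverse event tables.

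**What to change.** Replace the note in SAP 5.14.5 with wording such as:

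> For a hospitalization with no recorded discharge date, discharge is imputed as the earliest of death, data cutoff and the last date on which hospitalization status was assessed. That last date is no later than the short-term follow-up visit, or 30 days after the discontinuation decision if there was no visit. The number of imputed stays is reported by treatment arm.

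Recorded discharge dates after the visit can be kept; the change concerns imputed dates only. The cost is a short SAP edit, one line of programming and one count per arm, with no effect on trial conduct. The downside is that a genuinely long stay with no discharge date is undercounted. The count of imputed stays shows how far that could matter.

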5.14.6. Vital Signs, Physical Findings, and Other Observations Related to Safety

A summary of ECOG performance status at each scheduled time point will be provided. Actual value and change from baseline for vital sign measurements will be summarized at each assessment time point using summary statistics. Electrocardiogram (ECG) measurements will be summarized at each assessment time point using summary statistics. Listings of ECOG performance status, vital signs, and ECG data will be provided.

5.15. Pharmacokinetics and Immunogenicity

Serum concentrations of olaratumab prior to infusion (minimum concentration) and at 1 hour post-end of olaratumab infusion (approximately maximum concentration) will be summarized using descriptive statistics. Additional analysis utilizing the population PK approach may also be conducted if deemed appropriate. Relationships between olaratumab exposure and measures of efficacy and safety will be explored. A separate analysis plan will be provided for further PK analysis.

For immunogenicity, the number and percentage of patients with positive olaratumab antibody response will be summarized. Additional efficacy or safety analyses may be performed in the subgroup of patients with positive olaratumab antibody response. The antibody response and any alteration in olaratumab PK may also be explored, as well as any relationship with experiencing an infusion reaction. Further exploratory analyses may be performed as appropriate.

5.16. Translational Research

Planned translational research analysis includes the effect of platelet derived growth factor receptor α (PDGFR α) status on OS and PFS. PDGFR α status will be determined by using the Cell Signaling Technology rabbit monoclonal antibody (clone D13C6) proven to be specific for PDGFR α with no cross-reactivity for PDGFR β . This PDGFR α protein expression (pretreatment) immunohistochemistry is assessed at Lilly Clinical Diagnostics Laboratory in tumor cells, and was provided as a dichotomous variable with "positive" and "negative" expression, where a "positive" result shows at least 10% of the tumor (rounded to the nearest decile) demonstrating at least weak but specific membranous staining (1+ on a 0, 1+, 2+, 3+ scale of staining intensity). "Negative" corresponds to staining that does not meet these criteria. All other translational research analysis will be considered exploratory.

5.17. Interim Analysis

An IDMC will be established prior to first patient visit. The IDMC will review unblinded interim analyses of safety and efficacy data. These unblinded interim analyses will be performed by independent statistician. Only the IDMC and regulatory authorities are authorized to evaluate unblinded interim efficacy and safety analyses; Lilly (sponsor) will not be unblinded until the final analyses. Information that may unblind the study during the interim analyses will not be reported to study sites or study team until the study has been unblinded.

All interim analyses will include complete assessments of safety-related data; one interim analysis will include efficacy analysis at 60% of target OS events. Patient enrollment will continue during the conduct of these analyses. The interim analyses will be performed as follows:

- An unblinded safety data review after approximately 40 evaluable patients in each arm. This review will be performed by IDMC.
- After the first safety data review, regular safety reviews will be conducted by the IDMC approximately every 6 months.
- An efficacy analysis for the interim OS analysis will be conducted by the IDMC after 194 OS events (60% of the final OS events) have been observed in the ITT population.
- At the interim efficacy analysis, a safety data analysis will also be performed.

The IDMC meeting will occur within 2 months of the interim data cutoff date. The details on the process flow/communication plan among study team, IDMC, and senior management are provided in the IDMC charter.

5.17.1. Interim Efficacy Analysis

One interim efficacy analysis will be performed on/after 194 OS events (60% of the final OS events) observed in the ITT population. This analysis will be performed in order to provide the IDMC and regulatory authorities an opportunity to review interim safety and efficacy data together. There will be no formal statistical hypotheses tested at the interim for primary and secondary efficacy outcomes. There will be no alpha-spending associated with the interim analysis; study follow-up and data collection will continue as planned until the final analysis regardless of the nature of the interim efficacy results. Only the IDMC and regulatory authorities will be allowed access to unblinded interim data ; Lilly (sponsor) will not be unblinded to the interim analyses.

The following core analysis will be performed in addition to safety interim analysis described in Section [5.17.2](#):

Demographic and Other Baseline Characteristics

- patient demographics
- potential baseline prognostic factors
- baseline disease characteristics
- prior cancer therapies
- historical illness

Efficacy Analyses

- Kaplan-Meier survival curves and median survival and 95% CI for OS and PFS
- HR estimated using unstratified Cox PH model (because there will be many small cells for the primary Cox PH model at the time of the interim analysis) for OS and PFS
- PFS sensitivity analysis with different censoring rules according to [Table JGDJ.5.2](#)
- summary of ORR and DCR

5.17.2. Safety Interim Analysis

The following analyses will be performed for safety interim analysis, with analysis population as specified in [Table JGDJ.5.4](#).

Demographic and Other Baseline Characteristics

- patient demographics

Patient Disposition

- patient disposition
- reasons for treatment discontinuation as well as patients continuing on the study

Exposure

- summary statistics for exposure-related variables
- dose intensity of study drugs
- reasons for dose adjustments and dose delays

Adverse Events

- overview of AEs
- TEAEs summarized by PT*
- CTCAE v 4.0 Grade 3 or 4 or 5 AEs*
- SAEs summarized by PT*
- AESIs by PT*
- reasons for deaths
- AEs leading to study treatment discontinuations summarized by PT
- AEs leading to study treatment dose modification summarized by PT
- listing of SAEs
- listing of preexisting conditions and AEs

* Repeat for events deemed by the investigator to be possibly related to study medication.

Additional analyses may be conducted, at the request of the IDMC.

5.18. Clinical Trial Registry Analyses

Additional analyses will be performed for the purpose of fulfilling the Clinical Trial Registry (CTR) requirements. Analyses provided for the CTR requirements include the following:

- Summary of AEs, provided as a dataset which will be converted to an XML file. Both SAEs and “Other” AEs are summarized by treatment group and by MedDRA Preferred Term.
- An AE is considered “Serious” whether or not it is a TEAE.

- An AE is considered in the “Other” category if it is both a TEAE and is not serious.
- For each SAE and “Other” AE, for each term and treatment group, the following are provided:
 - the number of participants at risk of an event (if certain subjects cannot be at risk for some reason, for example, gender-specific AEs, then the number will be adjusted to only include the patients at risk)
 - the number of participants who experienced each event term
 - the number of events experienced.
- For each SAE, for each term and treatment group, the following are also provided for the EudraCT results submission:
 - The number of occurrences (events) causally related to treatment
 - The total number of deaths
 - The number of deaths causally related to treatment
- Consistent with www.ClinicalTrials.gov requirements, a threshold for frequency of “Other” AEs can be implemented rather than presenting all “Other” AEs. For example, “Other” AEs that occur in fewer than 5% of patients in any treatment group may not be included if a 5% threshold is chosen. The frequency threshold must be less than or equal to the allowed maximum of 5%.
- A participant flow will be created that will describe:
 - Number of participants per treatment arm. Screen failures do not need to be included. Number of participants who did not complete the study per treatment arm. This analysis will be based on study discontinuation, not treatment discontinuation.
 - Reasons participants did not complete the study.

5.19. Development Safety Update Report

The following reports are needed for the Development Safety Update Report (DSUR):

- Exposure information
- Listing of subjects who died during the DSUR period
- Discontinuations due to AEs during the DSUR Period

6. Unblinding Plan

This unblinding plan refers to the process to be followed for the final OS analyses.

Randomization will occur using an IWRS system. Assignment to treatment groups will be determined by a computer-generated random sequence. Security measures will be taken so that treatment group code and other variables that can link patients to study arm will be blinded in the database. This blinding will be maintained until the primary data lock.

Data sets will be created for the purpose of aggregate data review in which treatment assignment and related data, such as study drug administration dates and amounts, are scrambled so that personnel involved in the day-to-day conduct of the trial and development and validation of analysis programs will be blinded to patient treatment.

While every effort will be made to blind both the patient and the investigator to the identity of the treatment, the inadvertent unblinding of a patient may occur. This unblinding will not be sufficient cause (in and of itself) for that patient to be discontinued from study therapy or excluded from any safety or efficacy analysis.

[figure not shown]
In order to maintain the scientific integrity of this double-blind trial and the prospectively planned alpha-controlled analyses, access to study data will be strictly controlled. Treatment assignment will be scrambled in the reporting database until the database lock for final OS analysis.

7. References

- Akaike, H. Information theory and an extension of the maximum likelihood principle, in Petrov, B.N.; Csáki, F., *2nd International Symposium on Information Theory*, Akadémiai Kiadó, Budapest. 1973, pp. 267–281.
- Dolan P. Modeling valuations for EuroQol health states. *Med Care*. 1997;35(11):1095-1108.
- Farrar JT et al. Clinical importance of changes in chronic pain intensity measured on an 11-point numerical pain rating scale. *Pain*. 2001 Nov;94(2):149-58. Fleming TR. Interpretation of subgroup analyses in clinical trials. *Drug Information Journal*. 1995;29:1681S-1687S.

Appendix 1. Flow Chart of PFS Censoring Rules

Abbreviation: PD = progressive disease.

Appendix 2. List of Preferred Terms for AESIs

AESI	Preferred Term
Cardiac Dysfunction	Acute left ventricular failure
	Acute pulmonary oedema
	Acute right ventricular failure
	Cardiac asthma
	Cardiac failure
	Cardiac failure acute
	Cardiac failure chronic
	Cardiac failure congestive
	Cardiac failure high output
	Cardiogenic shock
	Cardiopulmonary failure
	Cardiorenal syndrome
	Chronic left ventricular failure
	Chronic right ventricular failure
	Cor pulmonale
	Cor pulmonale acute
	Cor pulmonale chronic
	Ejection fraction decreased
	Hepatic congestion
	Hepatojugular reflux
Left ventricular failure	
Low cardiac output syndrome	
Neonatal cardiac failure	

AESI	Preferred Term
	Obstructive shock
	Pulmonary oedema
	Pulmonary oedema neonatal
	Right ventricular failure
	Ventricular failure
	Artificial heart implant
	Atrial natriuretic peptide abnormal
	Atrial natriuretic peptide increased
	Brain natriuretic peptide abnormal
	Brain natriuretic peptide increased
	Cardiac cirrhosis
	Cardiac index decreased
	Cardiac output decreased
	Cardiac resynchronisation therapy
	Cardiac ventriculogram abnormal
	Cardiac ventriculogram left abnormal
	Cardiac ventriculogram right abnormal
	Cardiomegaly
	Cardio-respiratory distress
	Cardiothoracic ratio increased
	Central venous pressure increased
	Diastolic dysfunction
	Dilatation ventricular
	Dyspnoea paroxysmal nocturnal
	Heart transplant
	Hepatic vein dilatation

AESI	Preferred Term
	Jugular vein distension
	Left ventricular dysfunction
	Myocardial depression
	Nocturnal dyspnoea
	N-terminal prohormone brain natriuretic peptide abnormal
	N-terminal prohormone brain natriuretic peptide increased
	Oedema
	Oedema due to cardiac disease
	Oedema neonatal
	Oedema peripheral
	Orthopnoea
	Peripheral oedema neonatal
	Pulmonary congestion
	Right ventricular dysfunction
	Scan myocardial perfusion abnormal
	Stroke volume decreased
	Systolic dysfunction
	Venous pressure increased
	Venous pressure jugular abnormal
	Venous pressure jugular increased
	Ventricular assist device insertion
	Ventricular dysfunction
	Ventricular dyssynchrony
Cardiac Arrhythmias	Chronotropic incompetence
	Electrocardiogram repolarisation abnormality
	Electrocardiogram RR interval prolonged

AESI	Preferred Term
	Electrocardiogram U-wave abnormality
	Sudden cardiac death
	Bradycardia
	Cardiac arrest
	Cardiac death
	Cardiac telemetry abnormal
	Cardio-respiratory arrest
	Electrocardiogram abnormal
	Electrocardiogram ambulatory abnormal
	Electrocardiogram change
	Heart rate abnormal
	Heart rate decreased
	Heart rate increased
	Loss of consciousness
	Palpitations
	Rebound tachycardia
	Sudden death
	Syncope
	Tachycardia
	Tachycardia paroxysmal
	Bradyarrhythmia
	Ventricular asystole
	Accessory cardiac pathway
	Adams-Stokes syndrome
	Agonal rhythm
	Atrial conduction time prolongation

AESI	Preferred Term
	Atrioventricular block
	Atrioventricular block complete
	Atrioventricular block first degree
	Atrioventricular block second degree
	Atrioventricular conduction time shortened
	Atrioventricular dissociation
	Bifascicular block
	Brugada syndrome
	Bundle branch block
	Bundle branch block bilateral
	Bundle branch block left
	Bundle branch block right
	Conduction disorder
	Defect conduction intraventricular
	Electrocardiogram delta waves abnormal
	Electrocardiogram PQ interval prolonged
	Electrocardiogram PQ interval shortened
	Electrocardiogram PR prolongation
	Electrocardiogram PR shortened
	Electrocardiogram QRS complex prolonged
	Electrocardiogram QT prolonged
	Electrocardiogram repolarisation abnormality
	Lenegre's disease
	Long QT syndrome
	Sinoatrial block
	Trifascicular block

AESI	Preferred Term
	Ventricular dyssynchrony
	Wolff-Parkinson-White syndrome
	Nodal arrhythmia
	Nodal rhythm
	Sick sinus syndrome
	Sinus arrest
	Sinus arrhythmia
	Sinus bradycardia
	Wandering pacemaker
	Arrhythmia
	Heart alternation
	Heart rate irregular
	Pacemaker generated arrhythmia
	Pacemaker syndrome
	Paroxysmal arrhythmia
	Pulseless electrical activity
	Reperfusion arrhythmia
	Withdrawal arrhythmia
	Arrhythmia supraventricular
	Atrial fibrillation
	Atrial flutter
	Atrial parasystole
	Atrial tachycardia
	Junctional ectopic tachycardia
	Sinus tachycardia
	Supraventricular extrasystoles

AESI	Preferred Term
	Supraventricular tachyarrhythmia
	Supraventricular tachycardia
	ECG P wave inverted
	Electrocardiogram P wave abnormal
	Retrograde p-waves
	Anomalous atrioventricular excitation
	Cardiac flutter
	Extrasystoles
	Tachyarrhythmia
	Accelerated idioventricular rhythm
	Cardiac fibrillation
	Parasystole
	Rhythm idioventricular
	Torsade de pointes
	Ventricular arrhythmia
	Ventricular extrasystoles
	Ventricular fibrillation
	Ventricular flutter
	Ventricular parasystole
	Ventricular pre-excitation
	Ventricular tachyarrhythmia
	Ventricular tachycardia
	Allergic oedema
	Anaphylactic reaction
	Anaphylactic shock
	Anaphylactoid reaction

AESI	Preferred Term
	Anaphylactoid shock
	Angioedema
	Circulatory collapse
	Circumoral oedema
	Conjunctival oedema
	Corneal oedema
	Cytokine release syndrome
	Distributive shock
	Drug hypersensitivity
	Epiglottic oedema
	Eye oedema
	Eye swelling
	Eyelid oedema
	Face oedema
	First use syndrome
	Gingival oedema
	Gingival swelling
	Gleich's syndrome
	Hypersensitivity
	Idiopathic urticaria
	Infusion related reaction
	Kounis syndrome
	Laryngeal oedema
	Laryngotracheal oedema
	Limbal swelling
	Lip oedema

AESI	Preferred Term
	Lip swelling
	Oculorespiratory syndrome
	Oedema mouth
	Oropharyngeal swelling
	Palatal oedema
	Periobital oedema
	Pharyngeal oedema
	Scleral oedema
	Shock
	Swelling face
	Swollen tongue
	Tongue oedema
	Tracheal oedema
	Type 1 hypersensitivity
	Urticaria
	Urticaria cholinergic
	Urticaria chronic
Urticaria papular	
Infusion-related Reactions (9 additional PTs)	Abdominal pain
	Abdominal pain upper
	Abdominal pain lower
	Back pain
	Chills
	Dyspnoea
	Flushing
	Hypotension

	Pyrexia
--	---------

